As the risk of ACEI-associated angioedema is highest very shortly after treatment initiation and decreases over time ([Kostis et al 2005](#), [Miller et al 2008](#), [Toh et al 2012](#)), a cohort of prevalent ACEI users would be biased towards a lower angioedema risk compared to ACEI naïve patients. The majority of patients experiencing angioedema while treated with ACEIs can be expected to discontinue ACEI treatment and would therefore unlikely be part of a prevalent ACEI user cohort. Thus, comparing sacubitril/valsartan initiators regardless of their prior exposure to ACEIs/ARBs, to ACEI initiators who are treatment naïve to ACEIs and ARBs is likely to bias the comparative (explorative) analysis in favor of sacubitril/valsartan. Therefore, it is considered that the optimal comparison is between sacubitril/valsartan initiators who are treatment naïve to ACEIs/ARBs and ACEI initiators without prior ACEIs/ARB use. To provide an estimate of what may happen if prevalent users are included, we will explore all these analyses (see [Section 6.3](#) Exploratory objectives).

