Accruing the required sample size for the comparison of patients initiating sacubitril/valsartan treatment without prior ACEI/ARB use with those newly initiating treatment with ACEIs/ARBs within the proposed timelines will be very unlikely. It should be expected that many HF patients (both prevalent and incident) will have been previously exposed to an ACEI used as treatment for hypertension or other comorbid diseases prevalent in HF patients (e.g., acute myocardial infarction, diabetic nephropathy). A US study in patients with incident HF diagnosed between 2005 and 2008 from four sites participating in the Cardiovascular Research Network (CVRN) found an exposure prevalence to ACEIs or ARBs in patients with incident HFrEF (n=3,941, mean age 69 years) of 43% ([Goldberg et al 2013](#)). In the European ‘ESC-HF Long-Term Registry’ a prospective cohort study with primary data collection, including over 7,400 patients with prevalent chronic HF (median age 66 years) were enrolled over two years. In the subgroup of patients with HFrEF (n=4,792), 92.2% were treated with ACEIs or ARBs at baseline ([Maggioni et al 2013](#)). Thus, indicating that the absolute number of ACEI initiators who are treatment naïve to ACEIs and ARBs will be limited. If necessary, it was initially planned to supplement the contemporaneous comparator cohort with a historical cohort of ACEI initiators who are treatment naïve to ACEIs using data prior to Entresto® market approval if needed. However, the most recent interim report for the LCZ696B2014 study identified a total of 116,041 ACEI initiators being treatment naïve to ACEIs/ARBs [REDACTED] when both ARS and GePaRD were included. Based on these results, inclusion of a historical cohort of ACEI initiators treatment naïve to ACEIs/ARBs does not seem necessary.

In addition, to explore the impact of depletion of susceptibles we will assess the rate of events in users of ACEIs with prior use of ACEIs/ARBs.

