## 7.3 Variables

### 7.3.1 Exposures of interest

Exposures of primary interest are sacubitril/valsartan, ACEIs, and ARBs.

Exposure information will be identified using prescription or pharmacy fill data using the database specific coding system (e.g., Anatomical Therapeutic Chemical [ATC] Classification; British National Formulary [BNF]/Gemscript coding). Any use of ACEIs/ARBs will be included. The duration of each prescription/dispensing will be calculated by dividing the amount by the prescribed dose (if available) and otherwise by the national defined daily dose (DDD) equivalent by the World Health Organization (WHO). Episodes of treatment will be created for sacubitril/valsartan and for ACEIs/ARBs for all prescriptions in the same group if there are less than 90 days between the end of the previous prescription and the start of the new one. Overlap in prescriptions of the same kind will be disregarded (no ‘stockpiling’).

We will consider patients as ACEI- or ARB-naïve if they do not use an ACEI or ARB recorded within 365 days before the index date, respectively.

We will consider patients as having discontinued treatment if there is a gap in a series of successive prescriptions or pharmacy fills of the index drug class that is  $\geq 90$  days after the estimated treatment end of the last prescription or pharmacy fill preceding the gap. The calculated end of the prescription/dispensing will be defined as the date of discontinuation, at which point patients’ follow-up time will be censored. In the case where the follow-up ends before the 90 days are over a patient will not be considered to have discontinued.

Four exposure groups (cohorts) will be defined: two for sacubitril/valsartan-, and two for ACEI-users.

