#### 7.3.1.1 Sacubitril/valsartan user cohorts

- Sacubitril/valsartan initiators regardless of prior ACEI/ARB use (cohort 1)

This group includes all patients fulfilling the inclusion criteria ([Section 7.2.4](#)) and using sacubitril/valsartan during the study period – regardless of prior exposure to ACEIs or ARBs.

- Sacubitril/valsartan initiators treatment naïve to ACEIs/ARBs (cohort 2)

Cohort 2 is the subset of patients from cohort 1- who did not use ACEIs/ARBs in the 365 days prior to the index date.

---

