Sacubitril/valsartan treatment is likely to be initiated by specialists. CPRD and HSD have information on prescriptions from primary care only, but the other databases have data on dispensed drugs from both primary care and specialist outpatient care. Inpatient drug use is not available in any databases. This means that initiation of sacubitril/valsartan prescription (or pharmacy fill) may be missed if that took place in a setting not captured by the databases. Given that angioedema is more likely to occur shortly after treatment initiation, exposure misclassification may bias the results. Each of the databases carefully assessed how this type of bias can be mitigated, i.e. by verifying prescription (or pharmacy fill) durations, or examining referrals to specialists in the 3 months prior in the feasibility study ([section 7.1.2](#)). The time between referral or hospitalization for HF and first identified sacubitril/valsartan prescription (or pharmacy fill) in CPRD, HSD, GePaRD, and PHARMO was between 0 and 20 days for most sacubitril/valsartan users. In SIDIAP, this was more than 30 days for most patients. It seems plausible that for a number of these patients the first sacubitril/valsartan prescription may have been missed, either because inpatient prescribing is not present in all databases or outpatient specialist prescriptions are not captured (CPRD, HSD). The impact of misclassification of treatment start cannot be assessed with sensitivity analyses, because patients with an angioedema event during treatment that is not captured, will not have subsequent out-patient prescription records for sacubitril/valsartan that are captured, and therefore will not be included in the sacubitril/valsartan cohorts. If initiation of sacubitril/valsartan use is missed, but later exposure is captured, exposure time will be slightly underestimated and safety event rates may be slightly overestimated.

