There is a risk that prescribing sacubitril/valsartan may be channeled to patients with more severe HF, especially in the UK, where The National Institute for Health and Care Excellence (NICE) has issued a draft guidance recommending sacubitril/valsartan for treatment of chronic HfrEF in NYHA Class II-III symptom patients who take a stable dose of ACEIs and who have a left ventricular ejection fraction of 35% or less ([National Institute for Health and Care Excellence 2015](#)). To fully control for HF severity may be difficult as information on NYHA class or ejection fraction was not or only partially available across all databases and proxy measures for HF severity may not fully address this kind of channeling bias. This bias may specifically affect the comparative analyses for the relative risk assessment of angioedema (exploratory objectives, see [Section 6.3](#)). In addition, any choice of ACEIs (either prevalent or incident use) as comparator group, may be associated with some sort of bias. As indicated in the SmPC, sacubitril/valsartan is contraindicated in patients with a history of angioedema related to previous ACEI or ARB treatment or with hereditary or idiopathic angioedema. Thus,

patients initiating sacubitril/valsartan will likely have a low baseline risk of angioedema (since patients who experienced an angioedema event while on ACEI/ARB treatment should not be part of the sacubitril/valsartan patient pool). ACEI initiators who are treatment naïve to ACEIs/ARBs will, however, have a higher baseline risk of angioedema since this population includes all patients who are susceptible to an angioedema event. Thus, comparing sacubitril/valsartan initiators regardless of their prior exposure to ACEIs/ARBs to ACEI initiators who are ACEI/ARB treatment-naïve could bias the comparative analysis in favor of sacubitril/valsartan. However, the comparison of sacubitril/valsartan initiators who are treatment-naïve to ACEIs/ARBs versus ACEI/ARB treatment-naïve ACEI initiators which we consider the most accurate comparison, may be underpowered due to the small sample size of treatment-naïve sacubitril/valsartan initiators. The size of the cohort of ACEI/ARB treatment-naïve ACEI initiators was sufficiently large for any analyses, which is the reason why we considered the inclusion of a historical group of ACEI/ARB treatment-naïve ACEI initiators to be unnecessary.

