A comparison of sacubitril/valsartan users with prevalent ACEI users would likely bias against sacubitril/valsartan. In the group of prevalent ACEI users, the risk of angioedema can be expected to be relatively low, as patients with prior ACEI-associated angioedema should not be included, and patients with long term ACEI exposure have a lower risk as compared to new ACEI users (see also [Section 7.1.1](#)).

Misclassification of endpoints (safety events), as well as confounders is possible. For the different databases that will be used, validation studies have shown that coding is reliable in the databases and that these databases are suitable for pharmacoepidemiologic research. For those databases where free text is available (PHARMO, HSD, CPRD, and SIDIAP), validation of the safety events of interest will be conducted. Comparison of IRs of safety events of interest among databases in the quality run will allow checking for internal and external validity. The validation study will also assess validity in the other databases based on a patient profile review of available information.

For all databases, apart from Aarhus, it should be noted that the primary aim of data collection is patient management or reimbursement, and not medical research. This implies that only events are collected which are deemed to be relevant for patient care. In addition, information from specialists is incomplete in majority of the databases. The databases that capture all prescriptions or pharmacy fills (primary and secondary care) are Aarhus, PHARMO, ARS, and GePaRD. The other databases are primary care databases and do not capture (all) prescriptions from medical specialists. However, in all of these countries (UK, Italy, and Spain), prescriptions initiated by the specialist are generally continued by the GP.

Finally, there are differences in timing of data updates in the various databases (medical records are continuously updated, administrative databases are updated once per year in most instances). However, as data extraction will be repeated during the course of the study, this should allow for the most recent and “up-to-date” data to be used.

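### ACEI/ARB-naive status rests on prescription records that are incomplete in CPRD, HSD and probably SIDIAP, so some previously treated patients can enter cohorts 2 and 4 as naive there.

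*Protocol*

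**What the plan says.** **Definition.** Under section 7.3.1, patients count as ACEI- or "ARB-naïve if they do not use an ACEI or ARB recorded within 365 days before the index date". Section 7.3.1.1 applies this to sacubitril/valsartan: "Cohort 2 is the subset of patients from cohort 1- who did not use ACEIs/ARBs in the 365 days prior to the index date". Cohort 4 (section 7.3.1.2) applies the same 365-day rule to ACEI users.

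**Use.** The cohort 2 incidence rates are primary objective 2. Cohort 2 against cohort 4 is exploratory objective 1, of which section 7.1.1 says "it is considered that the optimal comparison is between sacubitril/valsartan initiators who are treatment naïve to ACEIs/ARBs" and new ACEI users without prior ACEI/ARB use.

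**Capture.** Section 7.9 names Aarhus, PHARMO, ARS and GePaRD as holding all primary- and secondary-care prescriptions or fills, and continues: "The other databases are primary care databases and do not capture (all) prescriptions from medical specialists". It adds that GPs in the UK, Italy and Spain generally continue what a specialist starts. It also says: "Inpatient drug use is not available in any databases".

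**SIDIAP.** An earlier paragraph of 7.9 limits the primary-care-only problem to CPRD and HSD, which puts SIDIAP among the databases with specialist outpatient data. Table 7-8 marks SIDIAP specialist prescriptions as incomplete, section 7.4.2 says they are missing, and the later paragraph of 7.9 leaves SIDIAP off the full-capture list.

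**What is discussed.** Sections 7.1.2 and 7.9 follow the capture gap through only for missed first prescriptions of sacubitril/valsartan. For the naive cohorts, 7.9 expects major problems of number and selection but names no mechanism of this kind.

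**The concern.** A missing record has opposite effects on the two drugs. A missed sacubitril/valsartan start delays or prevents cohort entry. A missed ACEI/ARB history moves a patient into the naive cohort.

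Section 7.1.1 argues that previously treated patients are depleted of those susceptible to angioedema. By that argument, falsely naive patients lower the cohort 2 rate, which is a primary-objective estimate. They can also bring back into exploratory objective 1 some of the depletion that the naive comparison was chosen to avoid.

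The effect is amplified when few starters are truly naive. Section 7.1.1 cites a European registry of prevalent heart failure in which, among patients with reduced ejection fraction, "92.2% were treated with ACEIs or ARBs at baseline". Section 7.9 cites draft UK guidance directed at "patients who take a stable dose of ACEIs" (and with low ejection fraction), so true naive starters may be few in CPRD. With a small true-naive group, even a modest loss of records makes up a large share of the apparent one.

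**Working it through.** **The plan's own figure.** Section 7.5 gives 132 cases in 24,000 patient-years, a rate of 5.5 per 1,000 (95% CI 4.6 to 6.5). An exact Poisson interval gives 5.50 (4.60 to 6.52), so it reproduces. It concerns sacubitril/valsartan exposure overall and is not affected by this point. The protocol gives no contamination figure for cohort 2.

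**Inputs**
- T, true share of prior ACEI/ARB users: 92.2% (European registry, prevalent disease) or 43% (US study, incident disease), both from 7.1.1. Neither was measured in sacubitril/valsartan starters.
- m, share of prior users with no record in the look-back: not in the protocol. Assumed 2%, 5% and 10%.
- Starters in feasibility (7.1.2): 5,185 in all, 4,724 in GePaRD (91.1%). That leaves 461 (8.9%), a count that still includes Aarhus, PHARMO and ARS.

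**Inside one affected database.** False share = T·m / [(1 − T) + T·m]. For T = 0.922 and m = 0.05: 0.0461 / (0.078 + 0.0461) = 0.371.

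**Pooled cohort 2, counting each patient once and treating all 461 as affected.** False share = 461·T·m / [5,185·(1 − T) + 461·T·m]. For T = 0.922 and m = 0.05: 21.25 / (404.43 + 21.25) = 0.050.

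| T | m | Affected database | Pooled |
|---|---|---|---|
| 92.2% | 2% | 19% | 2.1% |
| 92.2% | 5% | 37% | 5.0% |
| 92.2% | 10% | 54% | 9.5% |
| 43% | 2% | 1.5% | 0.1% |
| 43% | 5% | 3.6% | 0.3% |
| 43% | 10% | 7.0% | 0.7% |

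**Effect on the cohort 2 rate.** If prior users are assumed to have half the angioedema rate of naive users, the observed rate is multiplied by 1 − 0.5 × false share. At T = 92.2% and m = 5% this is 0.81 in an affected database and 0.975 pooled.

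**Effect on the hazard ratio.** Cohort 4 follows the same rule. In the five original databases the fourth interim report had more than 21,500 cohort 4 patients among more than 89,000 in cohort 3, an apparent naive share of about 0.242. With m = 5% the true share is (0.242 − 0.05) / 0.95 = 0.202, so about 1 − 0.202/0.242 = 17% of cohort 4 would be false. With the same half-rate assumption, the cohort 4 rate is multiplied by 1 − 0.5 × 0.165 = 0.92. The hazard ratio in an affected database is then multiplied by:
- 0.814 / 0.9175 = 0.89 if T = 92.2% in cohort 2;
- 0.982 / 0.9175 = 1.07 if T = 43% in cohort 2.

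So the direction, as well as the size, turns on inputs that the protocol does not supply.

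**Inpatient drugs.** This gap exists in all seven databases. It misclassifies only patients whose whole ACEI/ARB use in the year was in hospital, and its size cannot be computed from the protocol.

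**The case against.** The strongest defence is that the problem is small where it counts. Four of the seven databases, one of them with 91% of feasibility starters, are said to capture all outpatient fills. A falsely naive patient needs a full year without any captured ACEI or ARB, and GPs generally take over specialist prescriptions. Rates and hazard ratios are already planned per database (section 7.7.1.2.2), so CPRD, HSD and SIDIAP can be read on their own. The comparison is labelled exploratory and possibly underpowered, and details of pooling and sensitivity analyses are left to the SAP.

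Most of this stands, and it keeps the pooled effect modest. It does not remove the point. Continuation by the GP is stated as general, not universal. The cohort 2 rate is a primary objective with no comparator to offset the error. The per-database results are where the false share could be largest, and section 7.9 gives their reader no warning of it.

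A reader might infer that cohort 2 as a whole is contaminated and that exploratory objective 1 is therefore biased in favour of sacubitril/valsartan. The protocol does not support that. It gives no loss rate, the pooled share is small under most of the inputs tried, and cohort 4 carries the same error. Nor does it show that the full-capture databases must become the main analysis, which would be a trade-off against coverage.

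**Conclusion.** The mechanism is real and unaddressed: the definition of naive depends on records that are incomplete in CPRD, HSD and, by most of the protocol's statements, SIDIAP. Within such a database the false share of cohort 2 ranges from 1.5% to 54% over the inputs tried. Pooled, it is about 2% to 10% at 92.2% prior use and below 1% at 43%. The direction is downward for the cohort 2 rate. For the hazard ratio it is undetermined, because it depends on the difference in contamination between cohorts 2 and 4.

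These figures rest on an assumed loss of 2% to 10%, on prior-use shares from other populations, and on feasibility counts that may not match the final ones. The pooled figures weight patients equally; a meta-analysis could give the smaller databases more weight than their patient share. This is a cheap improvement to the plan and does not invalidate it.

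**What to change.** 1. Keep the planned pooled analysis. Add a pooled sensitivity analysis of primary objective 2 and exploratory objective 1, limited to the databases that 7.9 says capture primary- and secondary-care fills: Aarhus, PHARMO, ARS and GePaRD. If the SAP already contains it, a cross-reference is enough.
2. Reconcile the SIDIAP statements in Table 7-8, section 7.4.2 and the two paragraphs of 7.9, so that this set is fixed before the analysis. In the same pass, check the HSD entry in Table 7-8, which does not flag specialist prescriptions as incomplete, and section 7.4.6, which says that Aarhus lacks drugs dispensed directly to hospital patients or outpatient clinics.
3. Extend the 7.9 discussion of missed prescriptions to ACEI/ARB history. State that false naives are expected to lower the cohort 2 rate, that cohort 4 shares the rule, and that the net effect on the hazard ratio depends on the difference. Say also that the inpatient gap remains in every database.

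Excluding recently hospitalised patients is a weaker check. Hospital data cover about 55% of CPRD and 33% of SIDIAP, and in HSD depend on patient report.

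**Cost.** A database filter, one more analysis and some wording. At 92.2% prior use, patients lost from apparent cohort 2 are at most 461·[(1 − T) + T·m] / [5,185·(1 − T) + 461·T·m]. That is 36/404 = 8.9% with no loss of records and 78.5/446.9 = 17.6% at m = 10%, so roughly 9% to 18%. These are upper limits, because the 461 include Aarhus, PHARMO and ARS patients who would stay in.

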### 7.3.1.2 ACEI user cohorts

- ACEIs – users regardless of prior ACEI/ARB use (cohort 3)

[figure not shown]
This group includes all patients fulfilling the inclusion criteria ([Section 7.2.4](#)) and using ACEIs during the study period – regardless of prior exposure to ACEIs or ARBs. This cohort will be a mix of prevalent and incident ACEI users.

- ACEIs – without prior use of ACEI/ARB - treatment-naïve (cohort 4)

Cohort 4 is the subset of patients from cohort 3. It includes patients who did not use ACEIs/ARBs in the 365 days prior to index date. This sub-cohort corresponds to new ACEIs users - naïve to ACEIs/ARBs.

Note: Patients can be included in more than one cohort. Patients changing from ACEI to sacubitril/valsartan will be included in the corresponding ACEI cohort, as well as the sacubitril/valsartan cohort (only the first change will be considered). Patients changing from sacubitril/valsartan to an ACEI, however, will be censored. [Figure 7-2](#) illustrates cohort allocation and start of follow-up based on various exposure scenarios for sacubitril/valsartan and ACEI users.

**Figure 7-2 Cohort allocation based on various exposure scenarios for sacubitril/valsartan and ACEI users**

sac/val = sacubitril/valsartan; ACEI = angiotensin converting enzyme inhibitor; ARB = angiotensin receptor blocker; index date = date of first prescription or pharmacy fill of sacubitril/valsartan (cohort 1 & 2) or ACEI use (cohort 3 & 4) (not shown for the excluded patients); HF = heart failure (diagnosis must be recorded at any time prior or within 3 months after index date)

**Table 7-2 Study exposure sub cohorts, by study objective**

Study objective	Sub cohorts			
	Cohort 1 (any sacubitril/ valsartan)	Cohort 2 (sacubitril/ valsartan, no prior ACEI/ARB)	Cohort 3 (any ACEI)	Cohort 4 (ACEI, no prior ACEI/ARB)
Primary, no 1 (IRs of specific safety events of interest in HF patients newly starting treatment with sacubitril/valsartan [regardless of prior use of ACEIs or ARBs])	✓	--	--	--
Primary, no 2 (IRs of specific safety events in HF patients newly starting treatment with sacubitril/valsartan [without prior exposure to ACEIs or ARBs])	--	✓	--	--
Secondary, no 1 (IRs specific safety events in HF patients newly starting treatment with ACEIs [without prior exposure to ACEIs/ARBs])	--	--	--	✓
Secondary, no 2 (IRs specific safety events in HF patients with ACEI use [(regardless of prior use of ACEIs or ARBs)])	--	--	✓	--
Exploratory, no 1 (RR assessment of angioedema in adult HF patients newly starting treatment with sacubitril/valsartan [without prior ACEI/ARB exposure] compared to adult HF patients with ACEI exposure [without prior ACEI/ARB exposure])	--	✓	--	✓
Exploratory, no 2 (RR assessment of angioedema in adult HF patients newly starting treatment with sacubitril/valsartan [regardless of prior ACEI/ARB exposure] versus adult HF patients newly starting treatment with ACEIs [without prior ACEI/ARB exposure])	✓	--	✓	--

Exploratory, no 3 (RR assessment of angioedema in adult HF patients newly starting treatment with sacubitril/valsartan [regardless of prior ACEI/ ARB exposure]) versus adult HF patients with ACEI exposure [regardless of prior ACEI/ARB exposure])	✓	--	--	✓
---	---	----	----	---

ACEI = angiotensin converting enzyme inhibitor; ARB = angiotensin receptor blocker; HF = heart failure; RR = relative risk, IR = incidence rate

